2. SYNOPSIS

Title of Study:	Prospective, Multicenter, Post-Market 1 year Clinical Follow-up Study to evaluate safety and performance of the SUTUREFIX ULTRA and SUTUREFIX CURVED Suture Anchors in shoulder and hip arthroscopic repair
Study Design:	
 • Prospective • Approximately 8 sites: 
 - 4 sites for hip group - 4 sites for shoulder group • Two-arms (hip and shoulder)
Study Type:	Post-market study
Study Product:	SUTUREFIX ULTRA and SUTUREFIX CURVED Suture Anchor
Study Purpose:	Prospective, multicenter, post-market clinical follow-up to support CE Mark certification and Notified Body (BSI) for the Shoulder and Hip repair indications. Data to confirm safety and performance levels acceptable for the risk benefit profile of the devices.
Primary Objective:	To demonstrate the performance of the SUTUREFIX ULTRA and SUTUREFIX CURVED Suture Anchors in hip and shoulder for arthroscopic treatment over a time period of 6 months after arthroscopy.
Secondary Objective:	To assess safety and performance, supporting the use of SUTUREFIX ULTRA and SUTUREFIX CURVED Suture Anchors in hip and shoulder arthroscopy repair.
Statistical Rationale:	The study sample was decided based on the feasibility of recruitment, enrolment and follow-up considerations. The study is therefore not powered for any statistical testing but will be able to estimate a success rate of 86% with a 95% confidence interval (CI) [75: 97]. Previous studies suggest that the success rate among patients who have undergone any Suture Anchors for arthroscopic

Suturefix Ultra Suture Anchor	
Suturefix Curved Suture Anchor	
Prospective, Multicenter, Post-Market 1 year Clinical Follow-up Study to evaluate safety and performance of the SUTUREFIX ULTRA and SUTUREFIX CURVED Suture Anchors in shoulder and hip arthroscopic repair	Number: 17-5010-06
	Version: 1.0, 09/MAY/2018
	Page: Page 5 of 87

	instability repair is 71-97%.
Sample Size:	A total of 80 subjects; 40 subjects for the shoulder group and 40 subjects for the hip group, will receive at least one device, SUTUREFIX ULTRA and/or SUTUREFIX CURVED Suture Anchor. A sample size of 40 subjects will estimate a success rate of 89% with a 95% confidence interval (CI) [78: 100] with 55% probability.
Number of Study Sites:	Approximately 8 sites: 
 • 4 sites for study hip group • 4 sites for study shoulder group
Targeted Global Regions:	Europe

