8.3 STUDY ENDPOINTS

8.3.1 Primary Endpoint

- Clinical success rate, defined as subjects without signs of failure and/or re-intervention at 6 months, as assessed by the surgeon

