8.3.2 Secondary Endpoints

- Clinical success rate, defined as subjects without signs of failure and/or re-intervention at 12 months, as assessed by the surgeon
- Intra-operative anchor deployment success rate
- Number of anchors pulled out
- Use of additional anchors as a result of intra-operative failure
- Device-related re-intervention
- Safety evaluation at all time points
- Post-operative clinical success rate and performance assessed with subject reported outcomes as follows:

All subjects:

- Subject pain assessment with VAS at 6 months* and 12 months*
- Subject satisfaction assessment with VAS at 6 months* and 12 months*
- EQ-5D Questionnaire at 6 months* and 12 months*

Suturefix Ultra Suture Anchor Suturefix Curved Suture Anchor	
Prospective, Multicenter, Post-Market 1 year Clinical Follow-up Study to evaluate safety and performance of the SUTUREFIX ULTRA and SUTUREFIX CURVED Suture Anchors in shoulder and hip arthroscopic repair	Number: 17-5010-06 Version: 1.0, 09/MAY/2018 Page: Page 36 of 87

Hip subjects:

- Hip Outcome Score Activities of Daily Living (HOOS-ADL) at 6 months* and 12 months*
- Modified Harris Hip Score (HHS) at 6 months* and 12 months*

Shoulder subjects:

- ROWE Shoulder Scores at 6 months* and 12 months*
- ASES Shoulder Scores at 6 months* and 12 months*
- Constant-Murley Shoulder Scores at 6 months* and 12 months*

** Patient Reported Outcomes (PROs) are optional and used according to the surgeon's preference*

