9. STUDY PROCEDURES

9.1 VISITS AND EXAMINATIONS

9.1.1 Summary

For a summary of the required procedures by visit, refer to Table 9.1-1: Study Procedures by Visit

Table 9.1.1-1: Study Procedures by Visit

Schedule of events (*as needed)	Visit 1	Visit 2	Visit 3 Visit	Visit 4 Telephone Call or Visit	Visit 5 Unscheduled Visit
	Pre-Operative	Operative through Discharge	6 Months (± 1 M)	12 Months (± 1 M)	
Informed Consent	√				
Inclusion/Exclusion Criteria	√				
Demographics/ Medical History	√				
Intra-op failure as assessed by the surgeon		√			
Operative through Discharge		√			
Post-op Repair failure			√	√	√
All subjects					
Pain assessment with VAS	√**		√**	√**	√**
Satisfaction assessment with VAS	√**		√**	√**	√**
EQ-5D questionnaire	√**		√**	√**	√**
Hip					
HOOS-ADL score	√**		√**	√**	√**
Mod. Harris Hip score	√**		√**	√**	√**
Shoulder					
ROWE score	√**		√**	√**	√**
ASES score	√**		√**	√**	√**

Study Protocol—Device	
Prospective, Multicenter, Post-Market Clinical Follow-up Study to evaluate safety and performance of the SUTUREFIX ULTRA and SUTUREFIX CURVED Suture Anchors in shoulder and hip arthroscopic repair	Number: 17-5010-06
	Version: 0.17, 17/APR/2018
	Page: Page 38 of 87

Schedule of events (*as needed)	Visit 1	Visit 2	Visit 3 Visit	Visit 4 Telephone Call or Visit	Visit 5 Unscheduled Visit
	Pre-Operative	Operative through Discharge	6 Months (± 1 M)	12 Months (± 1 M)	
Constant-Murley score	√**		√**	√**	√**
MRI / Imaging	√		√*	√*	√*
Adverse Event Assessment		√		√	
End of Study/Exit				√	

* If needed to investigate repair failure

** Patient Reported Outcomes (PROs) are optional and used according to the surgeon's preference

Study Protocol—Device	
Prospective, Multicenter, Post-Market Clinical Follow-up Study to evaluate safety and performance of the SUTUREFIX ULTRA and SUTUREFIX CURVED Suture Anchors in shoulder and hip arthroscopic repair	Number: 17-5010-06
	Version: 1.0, 09/MAY/2018
	Page: Page 39 of 87

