9.1.2 Visit 1: Pre-Operative Visit

- Obtain written informed consent from the subject as detailed in Section 7.5
----- Do not proceed until consent has been obtained -----
- Obtain demographic information and medical history, including information on all concomitant medications/therapies
- Screen the subject for protocol inclusion/exclusion criteria
- Assign the subject a study number and instruct the subject on treatment procedures
- Complete Screening and Enrollment Log
- Complete VAS-Scale for Pain for all subjects*
- Complete EQ-5D questionnaire for all subjects*
- Complete ROWE Score for shoulder*
- ASES Score for shoulder*
- Complete Constant-Murley Score for shoulder*
- Complete HOOS-ADE Score for hip*
- Complete Modified HSS Score for hip*
- Perform MRI, only in case of repair failure
- If any adverse events are observed or reported, they must be recorded as instructed in Section 12.3, adverse events and device deficiencies
- Complete Pre-Operative Visit CRFs

**Patient Reported Outcomes (PROs) are optional and used according to the surgeon's preference.*

Study Protocol—Device	 smith&nephew
Prospective, Multicenter, Post-Market Clinical Follow-up Study to evaluate safety and performance of the SUTUREFIX ULTRA and SUTUREFIX CURVED Suture Anchors in shoulder and hip arthroscopic repair	Number: 17-5010-06
	Version: 1.0, 09/MAY/2018
	Page: Page 40 of 87

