9.1.4 Visit 3: 6-Month Follow-up Visit (\pm 1 month)

- Query subject regarding any changes in general health and the use of concomitant medications.
- If any adverse device effects or device deficiencies are observed or reported, they must be recorded as instructed in Section 12.3, adverse events and device deficiencies
- Post-operative repair failure
- Complete VAS-Scale for Pain and Satisfaction for all subjects*
- Complete EQ-5D questionnaire for all subjects*
- Complete ROWE Score for shoulder*
- ASES Score for shoulder*
- Complete Constant-Murley Score for shoulder*
- Complete HOOS-ADE Score for hip*

Study Protocol—Device	
Prospective, Multicenter, Post-Market Clinical Follow-up Study to evaluate safety and performance of the SUTUREFIX ULTRA and SUTUREFIX CURVED Suture Anchors in shoulder and hip arthroscopic repair	Number: 17-5010-06
	Version: 1.0, 09/MAY/2018
	Page: Page 41 of 87

- Complete Modified HSS Sore for hip*
- Perform MRI/Imaging only in case of repair failure
- Complete 6-Months Follow-up Visit CRFs
- Instruct the subject on follow-up procedures, including scheduling a FU call or visit in (\pm 1M) 12 months

**Patient Reported Outcomes (PROs) are optional and used according to the surgeon's preference.*

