The subject responses to each dimension score and the overall EQ-5D-5L index utility scores and EQ VAS scores will be summarized at baseline and all post-operative visits for the entire sample, by device type implanted and as well as the position, i.e. the hip or the shoulder.. The change in EQ-5D-5L index utility score and the change in EQ VAS score between baseline and all post-op visits will also be summarised.

EQ-5D-5L Utility scores and EQ VAS scores will be assessed using separate repeated measures ANOVA model, with the relevant score as the dependent variable for on entire sample with device implanted and position accounted for as levels in the model.

Hip subjects

- Hip Outcome Score Activities of Daily Living (HOOS-ADL) at 6 months* and 12 months*

Study Protocol—Device	 smith&nephew
Prospective, Multicenter, Post-Market Clinical Follow-up Study to evaluate safety and performance of the SUTUREFIX ULTRA and SUTUREFIX CURVED Suture Anchors in shoulder and hip arthroscopic repair	Number: 17-5010-06
	Version: 1.0, 09/MAY/2018
	Page: Page 49 of 87

- Modified Harris Hip Score (HHS) at 6 months* and 12 months*
 - The HOOS and HHS scores at different time points and end of study will be will be summarized for the entire sample and device implanted using median, SD, minimum, and maximum. A one sample t-test will be used to test the difference between baseline and end of study scores.

Shoulder subjects

- ROWE Shoulder Scores at 6 months* and 12 months*
- ASES Shoulder Scores at 6 months* and 12 months*
- Complete Constant-Murley Score for shoulder* at 6 months* and 12 months*
 - The ROWE and Constant-Murley Shoulder scores at different time points and end of study will be will be summarized for the entire sample and device implanted using mean, median, SD, minimum, and maximum. A one sample t-test will be used to test the difference between baseline and end of study scores. A non-parametric test will be considered if necessary.

**Patient Reported Outcomes (PROs) are optional and used according to the surgeon's preference*

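### Every score behind the score-based secondary performance endpoint is optional at the surgeon's preference, with no rule fixing that choice before the outcome is known and no completion report

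*Combined protocol and SAP*

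**What the plan says.** The last of the seven secondary endpoints in section 8.3.2 is "Post-operative clinical success rate and performance assessed with subject reported outcomes as follows". It lists eight instruments, each marked at 6 and 12 months with the footnote "Patient Reported Outcomes (PROs) are optional and used according to the surgeon's preference". The synopsis and section 5.2.1 repeat the mark. The schedule in section 9.1.1 carries it at Visits 1, 3, 4 and 5, which are all the visits where a score is scheduled.

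The visit sections read as if collection were universal: section 9.1.2 has "Complete VAS-Scale for Pain for all subjects" and section 9.1.4 has "Complete VAS-Scale for Pain and Satisfaction for all subjects". Each line ends in the asterisk that makes it optional. The footnote names only patient-reported outcomes, yet the mark also covers ROWE and Constant-Murley, whose forms in Appendix 21.4 grade motion and, for Constant-Murley, abduction strength.

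The surgeon also judges the repair. The primary endpoint in section 8.3.1 is "Clinical success rate, defined as subjects without signs of failure and/or re-intervention at 6 months, as assessed by the surgeon", and the 12-month success rate is assessed in the same way. In the schedule, "Post-op Repair failure" has a plain tick at Visits 3, 4 and 5, with no optional mark.

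Section 10.4.2 summarises pain, satisfaction, EQ-5D and the joint scores for the whole sample, and says "A one sample t-test will be used to test the difference between baseline and end of study scores". It adds a repeated measures ANOVA for EQ-5D-5L. ASES is listed there, but the sentence describing the shoulder analysis names only ROWE and Constant-Murley. Section 10 gives no completion table, minimum completion or missing-data method for the scores.

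**The concern.** The protocol does not say whether the preference is exercised once per site, per instrument, per subject or per visit. At Visits 3 and 4 the repair-failure assessment and the optional scores fall at the same contact, so the text permits a surgeon to decide on scoring after seeing how the patient has done. If patients who did well are scored more often, the mean change from baseline improves because of who was scored. The study has no control group to reveal or offset this.

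At stake is the part of the evidence that gives the patient's own account of pain, function and satisfaction, in a study meant to support CE Mark certification. A later SAP, due before database lock, cannot recover scores that were never taken.

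**Working it through.** **The plan's own figure.** Section 11 states a 55% probability that 40 subjects give a 95% interval of half-width 11 points at a true success rate of 89%. With exact (Clopper-Pearson) limits, 36 of 40 successes gives 76.3 to 97.2 (half-width 10.4) and 35 of 40 gives 73.2 to 95.8 (half-width 11.3). The probability is therefore P(X ≥ 36) for X ~ Bin(40, 0.89), which is 0.547. The figure reproduces. It concerns the success rate only and does not depend on the scores.

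**Inputs for the illustration.**
- From the documents: n = 40 per joint, and 11% failures (1 − 0.89, section 11).
- Assumed, because the documents give no figures: completion s in successes and f in failures; failures scoring D = 1 to 2 SD worse; SD 1 within each group; no true mean change overall.

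**Shift in the observed mean.** The share of failures among scored subjects is q = 0.11f / (0.11f + 0.89s), and the shift is (0.11 − q) × D.
- 90% against 50%: q = 0.055 / (0.055 + 0.801) = 0.064. The shift is 0.046 × D, or 0.05 to 0.09 SD.
- 80% against 20%: q = 0.022 / (0.022 + 0.712) = 0.030. The shift is 0.080 × D, or 0.08 to 0.16 SD.
- 100% against 0%: q = 0. The shift is 0.11 × D, or 0.11 to 0.22 SD.
- 50% in both: q = 0.055 / 0.500 = 0.11. The shift is 0.

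**False improvement.** This is the proportion of simulated studies in which the one-sample t-test rejects upward at two-sided 5%; the nominal rate is 2.5%.

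| Completion, successes / failures | Shift (SD) | False improvement |
|---|---|---|
| 50% / 50% | 0 | about 3% |
| 90% / 50% | 0.05–0.09 | about 4–8% |
| 80% / 20% | 0.08–0.16 | about 6–13% |
| 100% / 0% | 0.11–0.22 | about 9–25% |

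The last row can be checked by hand. About 0.89 × 40 = 35.6 subjects are scored, so the noncentrality is 0.11 × √35.6 = 0.66 or 0.22 × √35.6 = 1.31. Against a critical t of 2.03 these give about 9% and 25%. A separate simulation of this row gave 8 to 22%, so it should be read as approximate.

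**Selection directly on the score.** Suppose overall completion is 70% and depends on the change itself through a logistic curve. With 80% completion at 1 SD above the mean change and 60% at 1 SD below, the shift is 0.14 SD and false improvement 11 to 12%. With 88% against 50%, it is 0.25 SD and about 28%.

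**Precision.** Even without bias, optional collection costs information. The 95% half-width of a mean is 1.96/√n: 0.31 SD with 40 scores, 0.36 with 30, 0.44 with 20 and 0.62 with 10.

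**The case against.** The best defence is that the footnote may mean only that each surgeon or site picks the instruments already in routine use. Section 8.1 says data are recorded from the medical file, which fits that reading. If the choice is fixed in this way and does not vary with outcome within a site, the selection modelled above does not arise. This stands: per-patient selection is permitted by the text, but not stated.

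A reader might infer that the study's performance objective as a whole rests on selectively collected data. The documents do not support that. In the synopsis the primary objective is performance "for arthroscopic treatment over a time period of 6 months after arthroscopy", and its endpoint is the clinical success rate, which is not optional. Nor are 12-month success, deployment success, anchors pulled out, additional anchors, device-related re-intervention or safety. Nor are the scores the only data apart from the surgeon's success judgement: re-interventions, pull-outs and adverse events are recorded as events.

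A reader might also conclude that no analysis could correct the bias. If scoring follows the recorded success or failure, stratifying or weighting by that status can reduce it, provided some failures are scored. It would not help if scoring depends on something unrecorded.

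Sections 8.4 and 10.1 call the tests exploratory and unpowered, and section 8.4 asks for caution. That limits the weight placed on a p-value, but without completion figures a reader cannot tell how much caution is needed. Section 8.2 mentions an evaluator blinded to treatment group. That role is not defined and does not govern who is scored.

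**Conclusion.** The point holds for the score-based secondary endpoint only. The protocol leaves collection of all eight scores to the surgeon's preference, does not fix that preference before the outcome is known, and then plans whole-sample analyses of change with no account of who was scored. Selective scoring is an open risk, not an established fact.

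Its size depends on completion rates the documents do not give. If selection works through the surgeon's success judgement, the shift is modest (0.05 to 0.16 SD, false improvement about 4 to 13%) unless failures go entirely unscored (up to 0.22 SD and about 25%). The 28% figure needs strong selection on the score itself and should not be read as the expected case. If completion is unrelated to outcome, only precision is lost. The change is worth making before enrolment; the primary analysis and the sample-size statement are unaffected.

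**What to change.** Replace the footnote with wording such as: *Each site declares at site initiation, before its first subject, which scores it will use. The declared scores are then collected in every subject of that site at each visit where the instrument can be administered: baseline, 6 and 12 months; satisfaction at 6 and 12 months only; scores needing physical examination at 12 months only when Visit 4 is in person, with the visit mode recorded.*

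The exceptions are needed because Visit 4 may be a telephone call, and because the satisfaction question concerns the surgery and so has no pre-operative value. The schedule ticks satisfaction at Visit 1 while section 9.1.2 omits it; the two should be aligned.

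In section 10.4.2:
- Summarise each score over the sites that declared it, and do not describe the result as the whole sample.
- Tabulate completion by visit and by surgeon-assessed success or failure.
- Label any score taken outside the declaration as descriptive only.
- State the analysis of ASES.

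The cost is the footnote, an entry at the site initiation visit already planned in section 14.3, a visit-mode field and one completion table. Sites that declare a score will have somewhat more form-filling. Surgeons keep their choice of instrument but lose per-patient discretion.

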8.4 METHODS USED TO MINIMIZE BIAS AND MAXIMIZE VALIDITY

The study is a prospective multi-centre non-comparative cohort study to demonstrate the performance of the SUTUREFIX ULTRA and SUTUREFIX CURVED Suture Anchors in hip and shoulder for arthroscopic treatment over a time period of 12 months after arthroscopy. The study is exploratory in nature and not powered for any statistical testing hence the results from the study will be interpreted with caution.

Biases naturally associated with exploratory non-comparative studies will be inevitable but the use of multiple recruitment centres and well defined inclusion/exclusion criteria ensures that the study is more representative of a larger population and varying backgrounds. The exploratory data analysis planned for the study which includes confidence intervals for the outcome summaries, a pre-defined confidence interval for the primary outcome and exploratory statistical models adjusting for potential confounding factors is designed to maximise the validity of the study results.

Suturefix Ultra Suture Anchor Suturefix Curved Suture Anchor	
Prospective, Multicenter, Post-Market 1 year Clinical Follow-up Study to evaluate safety and performance of the SUTUREFIX ULTRA and SUTUREFIX CURVED Suture Anchors in shoulder and hip arthroscopic repair	Number: 17-5010-06
	Version: 1.0, 09/MAY/2018
	Page: Page 37 of 87

9. STUDY PROCEDURES

9.1 VISITS AND EXAMINATIONS

9.1.1 Summary

For a summary of the required procedures by visit, refer to Table 9.1-1: Study Procedures by Visit

Table 9.1.1-1: Study Procedures by Visit

Schedule of events (*as needed)	Visit 1	Visit 2	Visit 3 Visit	Visit 4 Telephone Call or Visit	Visit 5 Unscheduled Visit
	Pre-Operative	Operative through Discharge	6 Months (± 1 M)	12 Months (± 1 M)	
Informed Consent	√				
Inclusion/Exclusion Criteria	√				
Demographics/ Medical History	√				
Intra-op failure as assessed by the surgeon		√			
Operative through Discharge		√			
Post-op Repair failure			√	√	√
All subjects					
Pain assessment with VAS	√**		√**	√**	√**
Satisfaction assessment with VAS	√**		√**	√**	√**
EQ-5D questionnaire	√**		√**	√**	√**
Hip					
HOOS-ADL score	√**		√**	√**	√**
Mod. Harris Hip score	√**		√**	√**	√**
Shoulder					
ROWE score	√**		√**	√**	√**
ASES score	√**		√**	√**	√**

Study Protocol—Device	
Prospective, Multicenter, Post-Market Clinical Follow-up Study to evaluate safety and performance of the SUTUREFIX ULTRA and SUTUREFIX CURVED Suture Anchors in shoulder and hip arthroscopic repair	Number: 17-5010-06
	Version: 0.17, 17/APR/2018
	Page: Page 38 of 87

Schedule of events (*as needed)	Visit 1	Visit 2	Visit 3 Visit	Visit 4 Telephone Call or Visit	Visit 5 Unscheduled Visit
	Pre-Operative	Operative through Discharge	6 Months (± 1 M)	12 Months (± 1 M)	
Constant-Murley score	√**		√**	√**	√**
MRI / Imaging	√		√*	√*	√*
Adverse Event Assessment		√		√	
End of Study/Exit				√	

* If needed to investigate repair failure

** Patient Reported Outcomes (PROs) are optional and used according to the surgeon's preference

Study Protocol—Device	
Prospective, Multicenter, Post-Market Clinical Follow-up Study to evaluate safety and performance of the SUTUREFIX ULTRA and SUTUREFIX CURVED Suture Anchors in shoulder and hip arthroscopic repair	Number: 17-5010-06
	Version: 1.0, 09/MAY/2018
	Page: Page 39 of 87

9.1.2 Visit 1: Pre-Operative Visit

- Obtain written informed consent from the subject as detailed in Section 7.5
----- Do not proceed until consent has been obtained -----
- Obtain demographic information and medical history, including information on all concomitant medications/therapies
- Screen the subject for protocol inclusion/exclusion criteria
- Assign the subject a study number and instruct the subject on treatment procedures
- Complete Screening and Enrollment Log
- Complete VAS-Scale for Pain for all subjects*
- Complete EQ-5D questionnaire for all subjects*
- Complete ROWE Score for shoulder*
- ASES Score for shoulder*
- Complete Constant-Murley Score for shoulder*
- Complete HOOS-ADE Score for hip*
- Complete Modified HSS Score for hip*
- Perform MRI, only in case of repair failure
- If any adverse events are observed or reported, they must be recorded as instructed in Section 12.3, adverse events and device deficiencies
- Complete Pre-Operative Visit CRFs

**Patient Reported Outcomes (PROs) are optional and used according to the surgeon's preference.*

Study Protocol—Device	 smith&nephew
Prospective, Multicenter, Post-Market Clinical Follow-up Study to evaluate safety and performance of the SUTUREFIX ULTRA and SUTUREFIX CURVED Suture Anchors in shoulder and hip arthroscopic repair	Number: 17-5010-06
	Version: 1.0, 09/MAY/2018
	Page: Page 40 of 87

